## 2.3 BENEFIT/RISK ASSESSMENT

For patients with RA, sarilumab 150 mg and 200 mg every 2 weeks by SC injection has demonstrated clinically meaningful reductions of inflammatory joint swelling and tenderness of RA, improvements in physical function, and reduced progression of joint damage as measured by radiography.

However, in clinical trials of patients with RA sarilumab was associated with an increased risk of infections, including serious infections. As with other immunomodulatory therapies for RA, serious and sometimes fatal infections have been reported on sarilumab.

For this study it is proposed to administer sarilumab IV to patients with a confirmed viral pneumonia for which no antiviral therapy has demonstrated effectiveness. However, the potential benefit of sarilumab for patients with COVID-19 is suppression of the cytokine storm which may be a more important and long-lasting contributor to lung damage than the viral infection itself. One of the features of coronavirus pneumonia is a local and systemic increase in activated neutrophils which function to eliminate the viral infection but also inflict collateral damage to the pulmonary epithelium (26). In this context the dose-related reduction of absolute neutrophil count (ANC) associated with IL-6 $\alpha$  inhibition may help to mitigate the coronavirus-induced neutrophilia.

Uncertainties associated with this study include the route of administration, IV, and the sarilumab 400 mg dose; both intended to increase  $C_{max}$  and decrease  $t_{max}$  compared to SC route. Given that changes in ANC of antibody-mediated sIL-6R $\alpha$  are dose-dependent, irrespective of route of administration, it is anticipated that sarilumab delivered IV will rapidly suppress ANC. Based on analyses of 7985.5 patient-years of sarilumab exposure collected over 7.3 years from 3358 clinical trial patients with RA, the incidence of infection and serious infection did not increase with increasing severity of neutropenia. ANC values on sarilumab were normal for the majority of infections occurring within 12 weeks after sample collection (3452/3943 [88%] and 370/434 [85%] of patients reporting infections from patients treated with sarilumab plus conventional anti-rheumatic disease-modifying drug and sarilumab monotherapy, respectively. Both observations support the consistent finding that low ANC is not associated with an increased rate of infection for patients treated with sarilumab.

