## 4 STUDY DESIGN

### 4.1 OVERALL DESIGN

This study is an adaptive phase 3, randomized, double-blind, placebo-controlled trial to evaluate the efficacy and safety of sarilumab in hospitalized adults with severe or critical COVID-19. The study will be conducted in Europe and other countries except in the United States (US) in up to 100 sites.

Patients will be randomized in a 2:2:1 allocation ratio to sarilumab 400 mg IV, sarilumab 200 mg IV, or placebo. The sarilumab 200 mg IV dose arm will be closed for patients enrolled after Amended Protocol 04 is implemented. Patients enrolled after implementation of Amended Protocol 04 will be randomized in a 2:1 allocation ratio to sarilumab 400 mg IV or placebo (Section 4.3). All patients will receive a single dose of study drug on Day 1. Patients may receive a second dose with study drug (based on the original treatment group assigned) 24 to 48 hours after the first dose, if

1. The Benefit Risk assessment by the investigator favors the administration of another dose of study drug without compromising safety (e.g., increase in LFTs, neutropenia)

AND

2. At least one of the following criteria is met:
  - Increase in fever or recurrence of fever compared to Day 1 OR
  - Increase or no change in FiO2 requirement compared to Day 1 OR
  - Requiring vasopressors, ECMO, or development of multi-organ dysfunction

The safety data from approximately the first 12 patients randomized (assuming a total of ~10 patients are dosed on the sarilumab doses of 200 mg IV or 400 mg IV) will be reviewed by an independent data monitoring committee (IDMC) after the last of these patients dosed reaches Day 7. Data on approximately the first 12 and 50 patients (regardless of severity of illness) with at least 7-days follow-up will be reviewed by the IDMC to determine if the study can continue with or without modification. Subsequently, the frequency of IDMC meetings will be determined following the first 2 IDMC meetings. In addition to these specific assessment times, the IDMC will actively monitor interim data to make recommendations about early study closure, changes to study arms, and/or the eligible patient population throughout the course of the study.

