## 4.2 SCIENTIFIC RATIONALE FOR STUDY DESIGN

### Rationale for Study Design

This Phase 3 study utilizes a double-blind to minimize potential for bias on the part of the investigator, patient, or sponsor. Whilst the double-blind is maintained the protocol allows for adaptation of the primary endpoint based on new or emerging information to manage the uncertainties regarding assessment, course and prognosis of pandemic COVID-19.

Because of the novelty of the SARS-CoV-2 pathogen, the ease with which it spreads within a community, the current absence of effective anti-viral therapies or vaccines, and still evolving knowledge regarding course of disease and risk factors for progression, there is no criterion of efficacy validated by health authorities to support authorization for use. An adaptive design is necessary to accommodate these multiple uncertainties during this global health crisis to make most efficient use of valuable participant data and investigator resources in the context of an ongoing pandemic while maintaining the rigor of a double-blind placebo-controlled comparison.

In the absence of treatments with demonstrated efficacy, a placebo control is warranted to distinguish the safety and tolerability of sarilumab from the background signs and symptoms of COVID-19 infection as well as evaluate its potential to reduce fever, reduce oxygen requirements, and improve clinical outcomes.

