### **4.3 JUSTIFICATION FOR DOSE**

#### **Rationale for dose selection**

The sarilumab IV doses of 200 mg and 400 mg for this study are based similar pharmacokinetic (PK), pharmacodynamic (PD), and safety profiles between sarilumab and tocilizumab and the dose of tocilizumab 400 mg IV included in (32) mentioned in Xinhua press release dated 7 March 2020 (32) based on a case series of 20 patients treated in China (30). The PK, PD and safety of sarilumab and tocilizumab were compared in several randomized trials. In a single-dose, open-label randomized trial the PK and PD were assessed in patients with RA randomized 1:1:1:1 to either 150 mg or 200 mg (SC) of sarilumab, or 4 mg/kg or 8 mg/kg (IV) of tocilizumab. In a single dose PK/PD study, 150 mg of sarilumab (SC) was compared to 162 mg of tocilizumab (SC) in Japanese patients with RA randomized 1:1 (33). In these single dose studies, consistent with saturation of the target-mediated pathway for sarilumab and tocilizumab, all dose levels regardless of the route of administration demonstrated similar maximal effect in suppression in CRP and ANC lowering. Higher dose levels and the associated higher concentrations beyond that need to achieve saturation, resulted in a longer duration of the maximal PD response, but did not result in a deeper response. Subcutaneous single doses of sarilumab (150 mg) or tocilizumab (162 mg) resulted in similar concentration time profiles and yielded nearly identical PD response in CRP and ANC, as well as changes in sIL-6R and IL-6 over time (34). Although PK/PD modeling suggested that the higher binding affinity to IL-6R $\alpha$  of sarilumab compared to tocilizumab translates to greater receptor occupancy (35), there is currently no detailed information available on sIL-6R $\alpha$  concentrations in patients with COVID-19. It is possible (perhaps probable) that peak concentrations of sIL-6R $\alpha$  in patients with COVID-19 may greatly exceed what has been measured in patients with RA; therefore, dose-finding above exposures yielded by SC of sarilumab are needed given the urgency to identify useful therapeutics for COVID-19.

Because the optimal dose regimen of sarilumab IV is unknown for treatment of patients with severe or critical COVID-19, the study includes two dose levels. In addition, a second infusion of sarilumab 200 mg IV, sarilumab 400 mg IV, or placebo can be administered under the conditions specified in [Section 4.1](#).

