### 9.4.1 General considerations

For continuous variables, descriptive statistics will include the following information: the number of patients reflected in the calculation (n), mean, standard deviation, Q1, median, Q3, minimum, and maximum.

For categorical or ordinal data, frequencies and percentages will be displayed for each category.

Subgroups will be defined by key baseline factors (eg, demographics, disease characteristics). Subgroup analyses will be performed on efficacy endpoints and safety endpoints, as needed. Details will be described in the SAP.

Statistical analyses will be performed using Statistical Analysis Software (SAS) version 9.4 or higher.

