- Any symptom of Fever, Cough, or Dyspnea (Yes, No)
- Time from dyspnea onset to baseline (≤ 5 days, > 5 days). Note: patients with no dyspnea will be classified as ≤ 5 days
- SpO₂/FiO₂ ratio (<median, >=median)
- CRP level (<median, >=median)
- Duration of hospitalization prior to first dose (< 7 days, ≥ 7 days);
- Number of study drug administration (1, 2)

Additional subgroups may be added as needed. The treatment effects will be estimated using hazard ratio (sarilumab compared to placebo) in the subgroups using the same analysis model as for the primary efficacy endpoint as described previously (without stratification factor for the stratification-related subgroups). In addition, p-value for the interaction of treatment by subgroup effect will be provided. Graphical presentation of the results (ie, forest plot) for each sarilumab dose versus placebo will also be provided.

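### The primary-endpoint subgroups include number of doses received, which is settled after treatment starts, so its hazard ratios and interaction p-value do not compare groups made alike by randomisation

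*SAP*

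**What the plan says.** SAP 2.4.4.1 gives 17 variables for subgroup analysis of the primary endpoint. The last is "Number of study drug administration (1, 2". For every variable the SAP plans a sarilumab/placebo hazard ratio within each level from the primary analysis model and a forest plot, and it adds that a "p-value for the interaction of treatment by subgroup effect will be provided". The section labels these analyses descriptive.

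Protocol 9.4.1 sets the general rule: "Subgroups will be defined by key baseline factors (eg, demographics, disease characteristics"). It leaves details to the SAP.

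Protocol 4.1 allows a second dose 24 to 48 hours after the first under two joint conditions. One is a judgement: "The Benefit Risk assessment by the investigator favors the administration of another dose of study drug without compromising safety", with liver tests and neutropenia as the examples. The other is at least one clinical trigger. The first trigger reads "Increase in fever or recurrence of fever compared to Day 1 OR"; the alternatives are a raised or unchanged FiO2 requirement, and a need for vasopressors or ECMO or the development of multi-organ dysfunction. Under Protocol 7.2, an infusion stopped for safety also rules out a second dose.

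**The concern.** A subgroup hazard ratio is a randomised comparison only if the subgroup is fixed before treatment can influence it. Dose count is not. The protocol sets out to "evaluate its potential to reduce fever, reduce oxygen requirements, and improve clinical outcomes" (Protocol 4.2), and fever and oxygen requirement are second-dose triggers. It also states that "it is anticipated that sarilumab delivered IV will rapidly suppress ANC" (Protocol 2.3), and neutropenia is named in the safety judgement. ALT increase is an adverse event of special interest (Protocol 8.3.6), and liver tests are named there too.

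If sarilumab averts some triggers, the sarilumab 1-dose group contains patients who would have been re-dosed on placebo. The sarilumab 2-dose group contains those who met the criteria despite active drug. Neither has a matching placebo group.

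At stake is interpretation. Protocol 4.3 says "Because the optimal dose regimen of sarilumab IV is unknown for treatment of patients with severe or critical COVID-19", and a reader looking for evidence on a second infusion would turn to these rows, which cannot supply it.

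**Working it through.** The plan attaches no figure to this row, so there is none to reproduce. The check compares the texts and then illustrates the bias under assumptions.

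**1. Is dose count a baseline factor?** SAP 2.1.1 defines baseline as the last value before the first dose. The other 16 listed variables all appear among the SAP 2.1.1 baseline characteristics. Dose count does not, and since it is settled 24 to 48 hours after the first dose it cannot meet the definition. SAP 1.5 and 1.6, which record statistical changes, do not mention it.

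**2. Which model applies to the row?** SAP 2.4.4.1 reuses the primary model and drops stratification only for subgroups built from the stratification factors. The dose-count row therefore keeps stratification by severity and corticosteroid use, and any illustration must allow for that.

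**3. How large could the bias be?** Every input below is assumed except the 45% placebo improvement by Day 15, the 160 vs 80 patients (Protocol 9.2) and the Day 29 cut-off.

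- Latent severity L ~ N(0,1).
- Trigger score E = ρL + √(1−ρ²)·noise, minus any treatment shift. A second dose is given if E exceeds a cut-off set so that 50% of placebo patients are re-dosed.
- Time to improvement is exponential with log-hazard proportional to −βL, calibrated to 45% on placebo by Day 15 and censored at Day 29.
- No treatment effect on the endpoint, and no added effect of the second dose. The true hazard ratio is 1.00; values above 1 favour sarilumab.
- Weak link: ρ = 0.4, β = 0.5. Strong link: ρ = 0.6, β = 1.0.

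A uniform shift of 0.67 SD lowers sarilumab re-dosing to P(Z > 0.67) = 25%. A 1.5 SD shift confined to the sicker half (L > 0) lowers it to about 21–24%.

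| Case (no true effect) | Analysis | 1-dose / 2-dose HR | Interaction rejections at 0.05 |
|---|---|---|---|
| No arm difference in re-dosing | unstratified | 1.00 / 1.00 | about 5% |
| Uniform shift, weak to strong | unstratified | 0.93/0.91 to 0.85/0.79 | about 5% |
| Uniform shift, weak to strong | stratum equal to L > 0 | 0.97/0.97 to 0.95/0.91 | – |
| Less-sick half only, weak to strong | unstratified | 1.04/0.78 to 1.02/0.67 | 14–19% |
| Sicker half only, weak | unstratified | 0.83 / 1.31 | about 23% |
| Sicker half only, weak | stratum correlated 0.7 with L | 0.88 / 1.20 | 14% |
| Sicker half only, weak | stratum equal to L > 0 | 0.98 / 0.97 | 5% |
| Sicker half only, strong | unstratified | 0.70 / 1.57 | about 55% |
| Sicker half only, strong | stratum correlated 0.7 with L | 0.77 / 1.41 | about 31% |
| Sicker half only, strong | stratum equal to L > 0 | 0.97 / 0.93 | about 6% |

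The interaction test asks whether the ratio of the two hazard ratios is 1. In the strong sicker-half case that ratio is 1.57/0.70 = 2.24, then 1.41/0.77 = 1.83, then 0.93/0.97 = 0.96 as the stratum captures more of the severity split. In the strong uniform-shift case, unstratified, it is 0.79/0.85 = 0.93. Rejection therefore stays near 5% although both rows are biased. A quiet interaction test is no assurance that the rows are sound.

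**4. Precision.** In the unstratified simulations the median standard error of the 2-dose log hazard ratio is 0.25–0.34. A 95% interval would reach a factor of exp(1.96 × 0.25) = 1.63 to exp(1.96 × 0.34) = 1.95 either side of the estimate, before any bias.

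**The case against.** The strongest reply has four parts.

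- **Limited weight.** The analyses are labelled descriptive, lie outside the hierarchy in SAP 2.4.4.3, and this is one variable of 17. This stands and limits the weight of the point. It does not repair the comparison, and the interaction p-value and forest plot set the row beside true baseline subgroups.
- **Room in the text.** Protocol 9.4.1 leaves details to the SAP, and SAP 2.4.4.1 allows further subgroups. True, but neither makes a post-dose variable a baseline factor. The statistical argument is in any case stronger than the document conflict.
- **Stratification.** The planned model for this row is stratified, so unstratified illustrations overstate the bias. This stands. Stratification reduces the bias by an amount that depends on how well severe/critical status and corticosteroid use capture prognosis, which is unknown. The case in which it nearly disappears is favourable by construction, because the stratum splits patients exactly where the assumed treatment effect does.
- **Extreme scenario.** The high false-positive rates need a 1.5 SD trigger effect confined to one half of patients, and no document figure supports that. Also true. A smaller unstratified sicker-half effect (0.5 SD, placebo re-dosing 40%) gives 0.93/1.07 to 0.87/1.09 and 7–8% rejections.

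A reader might also infer that the protocol introduced the second infusion because the best regimen is unknown. In Protocol 4.3 that clause explains the two dose levels, and the second infusion follows as an addition. The link is an inference from that section.

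**Conclusion.** The row is wrong as written. Dose count is settled after the first dose by factors that treatment may affect, it departs from the protocol's baseline rule without a stated reason, and its hazard ratios can be biased in either direction.

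Size and direction are unknown. The documents give no second-dose rates, and the simulated figures are illustrations, not bounds. Bias is absent if treatment leaves re-dosing unchanged. Otherwise the planned stratification reduces it by an unknown amount.

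Some stronger readings are not supported:

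- The primary test, its alpha and the hierarchy are not affected.
- A false-positive rate of about 55% should not be attached to this plan, because it comes from an unstratified model the SAP does not use here.
- The protocol does not say that neutrophils would fall far enough within 48 hours to prevent re-dosing.
- The safety summaries by number of doses in SAP 2.4.5 are offered only where appropriate and specify no between-arm hazard ratio. They are a separate matter.

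**What to change.** Delete the number of study drug administrations from the treatment-effect subgroups, interaction tests and forest plot in SAP 2.4.4.1. Keep the dose-count summaries by arm already planned in Protocol 9.4.7 and SAP 2.4.3.1. If outcomes by dose count are shown, present them within each arm, with no sarilumab/placebo hazard ratio or interaction p-value, labelled as groups selected after randomisation. The second-dose rule itself is not in question.

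The cost is a change of SAP wording before the primary database lock. One descriptive split is lost.

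A separate minor correction: the age bands in SAP 2.1.1 and 2.4.4.1 leave out patients aged 64 to under 65 and 84 to under 85. Make them contiguous: 18 to under 65, 65 to under 85, and 85 or over. The median-age split still covers every patient.

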2.4.4.2 Analyses of secondary efficacy endpoints

Key secondary endpoint

The percentage of patients alive at Day 29 will be analyzed using Cochran-Mantel-Haenszel (CMH) test stratified by randomization strata of severity of illness and corticosteroid use in the mITT population. The difference in proportions of patients for each Sarilumab dose compared to placebo (sarilumab - placebo), along with associated 2-sided 95% confidence levels, and p-value will be provided.

Superiority of sarilumab over placebo will be declared if the null hypothesis is rejected at the 5% (2-sided) significance level following the multiplicity control procedure specified in [Section 2.4.4.3](#).

In addition, bar plot for the proportion of patients alive at Day 29, KM curves for the overall survival will be provided by treatment group. Hazard ratios for the estimation of treatment effect of each sarilumab dose compared to placebo will be provided using Cox proportional hazards model stratified by the randomization stratum with treatment as a covariate, along with 2-sided confidence intervals.

These analyses will be repeated for the severe patients and critical patients at baseline as recorded on CRFs.

Other secondary endpoints

Details for analyses and derivation of the variables associated with the other secondary endpoints specified in [Section 2.1.3.2](#) are detailed below.

7-point ordinal scale

The percent of patients with each category of the 7-point ordinal scale observed value at each day will be summarized using descriptive statistics. Graphical presentations (stacked bar charts) will also be used to examine trends over time.

Analysis of endpoint #1: proportion of patients with one-point improvement from baseline

Proportion of patients with at least 1-point improvement from baseline at Day 4, 7, 15, 21, and 29 will be analyzed using the same analysis model as for the key secondary endpoint as described previously. Graphical presentations (bar charts) will be used to examine trends over time.

Analysis of endpoint #2: Mean change in 7-point ordinal scale from baseline

Changes from baseline in the 7-point ordinal scale for Day 4, 7, 15, 21, 29 (or until discharge) will be analyzed using an ANCOVA model with treatment group and randomization strata as fixed effects and baseline value as a covariate. The least squares (LS) treatment mean difference from placebo with standard error, along with corresponding 95 % confidence interval and p-value will be provided. Graphical presentations (line plot with mean and error bar) will also be used to examine trends over time using mean values (\pm SE) and mean changes from baseline (\pm SE).

The 7-point ordinal scale at each day and their changes from baseline will also be summarized for each treatment group through descriptive statistics including mean, median, standard deviation, minimum and maximum.

Fever

Body temperature is collected using varying methods (the routes in eCRF are axillary, auricular, oral, rectal) at multiple timepoints each day.

Baseline body temperature is defined as the highest temperature at any time prior to first dose.

Post-baseline body temperature is defined as the highest temperature from each day among all temperatures from different timepoints (morning, evening, etc).

Patients body temperature and its change from baseline will be summarized at each day by treatment group by timepoint over the study period. Graphical presentations (line plot with mean and error bar) will also be used to examine trends over time using mean values (\pm SE) and mean changes from baseline (\pm SE).

All temperatures will be converted to oral values as following:

- Rectal/Auricular subtract 0.6 deg C = Oral deg C
- Axillary add 0.6 deg C = Oral deg C

Analysis of endpoint #3: time to resolution of fever

Resolution of fever is defined as body temperature ($\leq 36.6^{\circ}\text{C}$ [axilla], or $\leq 37.2^{\circ}\text{C}$ [oral], or $\leq 37.8^{\circ}\text{C}$ [rectal or auricular]) for at least 2 consecutive days without antipyretics or until discharge, whichever is sooner.

The analysis will be performed similarly to the primary endpoint.

Patients who achieved resolution of fever or discharge (other than death) will be considered as events, while patients who do not experience resolution of fever will be censored at the end of study. Patients who started rescue therapy or died in the study will not be considered as having an endpoint event and will be censored at the earlier date of death or rescue therapy start date. Patients who do not have fever at baseline will be censored at the first dose date.

Analysis of endpoint #5: the number of days with fever

Fever is defined as body temperature $>37.4^{\circ}\text{C}$ (axillary), or $>38^{\circ}\text{C}$ (oral), or $>38.4^{\circ}\text{C}$ (rectal or auricular).

The number of days with fever will be analyzed using the ANCOVA model with treatment group and randomization strata as fixed effects for patients alive by Day 29. The LS treatment mean difference from placebo with standard error, along with corresponding 95 % confidence interval and p-value will be provided.

Summary statistics with mean, median, standard deviation, minimum and maximum will be provided. Histogram will be provided to illustrate the distribution of days with fever.

In addition, the percent of days with fever ($100 \times$ number of days with fever divided by number of days of follow-up, defined as the earlier date of death or discharge or last visit up to Day 29) for all patients, will be analyzed using the ANCOVA model with treatment group and randomization strata as fixed effects.

Improvement in Oxygenation

Improvement in oxygenation is defined as increasing in SpO₂/FiO₂ of 50 or greater compared to the nadir SpO₂/FiO₂. Nadir SpO₂/FiO₂ is the nadir (lowest value) at any point in the study, and looking forward, an improvement in oxygenation is increase of 50 or greater from nadir value for at least 48 hours. If nadir is observed on 2 or more different days post baseline, the day of the first occurrence of nadir will be used.

Baseline SpO₂/FiO₂ ratio is defined as the last available ratio prior to first dose.

Post-Baseline SpO₂/FiO₂ ratio is defined as the worst (minimum) value in each day.

For derivation of FiO₂, please see conversion table in [Section 2.5.2](#).

***Analyses of endpoint #4: time to resolution of fever and improvement in oxygenation,
#9: time to improvement in oxygenation, and
#14: time to saturation $\geq 94\%$ on room air***

The analysis of these endpoints will be performed similarly to the primary endpoint.

Patients who do not experience the event under analysis will be censored at the last observation time point. Patients who die or take rescue medication in the study without experiencing the event will be censored at the earlier date of death or rescue medication started.

***Analyses of endpoint #11: days of hypoxemia,
#12: days with supplemental oxygen use,
#13: days of resting respiratory rate >24 breaths/min, and
#15: ventilator free days in the first 28 days***

The analysis of these endpoints will be performed using the ANCOVA model with treatment group and randomization strata as fixed effects for patients alive by Day 29. The LS treatment mean difference from placebo with standard error, along with corresponding 95 % confidence interval and p-value will be provided. Patient discharged early will be considered as ventilator free until the next hospitalization (if applicable).

Summary statistics with mean, median, standard deviation, minimum and maximum will be provided. Histogram will be provided to illustrate the distribution.

In addition, the percent of days with each endpoint ($100 \times$ number of days with the endpoint divided by number of days of follow up, defined as the earlier date of death or discharge or last

visit up to Day 29) for all patients, will be analyzed using the ANCOVA model with treatment group and randomization strata as fixed effects.

Analyses of endpoint #10: % of patients alive off oxygenation at Day 29, and #16: % of patients with initiation of mechanical ventilation, non-invasive ventilation, or use of high flow nasal cannula, and

These endpoints will be analyzed using a Cochran-Mantel-Haenszel (CMH) test stratified by randomization strata. The difference in proportions of patients for each Sarilumab dose compared to placebo (sarilumab - placebo), along with associated 2-sided 95% confidence levels, and p-value will be provided.

Bar plots will also be provided to illustrate the difference among treatments.

NEWS2

Please find NEWS2 score calculation and details in [Section 2.5.2](#).

Analyses of endpoint #6: Time to change in National Early Warning Score 2 (NEWS2) from baseline, and #7: Time to NEWS2 of <2 and maintained for 24 hours

The analysis for time to change in NEWS2 from baseline will be performed by evaluating the proportion of patients with clinical risk over time in each category (Low: 0-4; Low-medium: 3 in any individual parameter; Medium: 5-6; High: ≥ 7). The pattern of patients in the categories shifting from baseline and over time will be examined with no formal testing.

The time to NEWS2 < 2 and maintained for 24 hours endpoint will be analyzed similarly to the primary endpoint.

Patients who do not experience endpoint event under analysis will be censored at the last observation time point. Patients who die or take rescue medication in the study without experiencing the event will be censored at the earlier date of death or rescue medication started.

Analyses of endpoint #8: Mean change from baseline to Day 4, 7, 15, 21, 29 in NEWS2

Change from baseline in NEWS2 score at Day 4, 7, 15, 21, and 29 will be analyzed using an ANCOVA model with treatment group and randomization strata as fixed effects, and baseline value as a covariate. The least squares (LS) treatment mean difference from placebo with standard error, along with corresponding 95 % confidence interval and p-value will be provided. Graphical presentations (line plot with mean and error bar) will also be used to examine trends over time using mean values (\pm SE) and mean changes from baseline (\pm SE).

NEWS2 score at each day and their changes from baseline will be summarized for each treatment group through descriptive statistics including mean, median, standard deviation, minimum and maximum.

ICU use, rescue medication, hospitalization and other

Analyses of endpoint #17: % of patients requiring rescue medication during the 28-day period, #18: % of patients with ICU use (among those not in an ICU at baseline)

These endpoints will be analyzed using a CMH method stratified by randomization strata. The difference in proportions of patients for each Sarilumab dose compared to placebo (sarilumab - placebo), along with associated 2-sided 95% confidence levels, and p-value will be provided.

Bar plots will be provided to illustrate the difference among treatments. Summary of immunosuppressive medications used as rescue therapy over time will also be provided.

Analyses of endpoint #19: Days of hospitalization among survivors

Analysis of days of hospitalization among survivors will be performed using the ANCOVA model with treatment group and randomization strata as fixed effects. The LS treatment mean difference from placebo with standard error, along with corresponding 95 % confidence interval and p-value will be provided.

Summary statistics with mean, median, standard deviation, minimum and maximum will be provided. Histogram will be provided to illustrate the distribution.

In addition, the percent of patients died or “on a ventilator”, off oxygenation, and discharged will be summarized by treatment overtime, respectively. The time from first dose to discharge will also be summarized.

